3.1 Purpose of the Clinical Trial

Through this real-world study, to analyze the response of functional constipation patients with different severity, treatment status, capsule dosage, and combined medication to Vibrabot capsule, as well as the duration of efficacy maintenance during the follow-up period; to compare the efficacy with patients treated with drugs or other therapies during the same period, explore the possibility of curing functional constipation patients, further improve the treatment satisfaction of constipation patients, and promote the establishment and application of consensus or guidelines for the use of Vibrabot capsule in treating functional constipation.

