3.2 Content of the Clinical Trial

This study is a multi-center clinical trial. Patients are considered eligible for this study if they meet the inclusion criteria and do not meet any of the exclusion criteria. This study plans to include 300 patients with chronic functional constipation to treat with Vibrabot capsules for at least 6 weeks, and ≥ 300 patients with constipation receiving

other treatments concurrently. The patients, based on their treatment needs and preferences, and after comprehensive consideration by clinical doctors, will undergo vibrating capsule treatment, other treatments, or combination therapy. After entering the study, patients should maintain stable dietary intake (including high-fiber diet, fiber supplements, probiotics, etc.) and exercise according to the recommendations of the constipation diagnosis and treatment guidelines.

During the entire clinical study period, patient-related information will be collected according to the specified time points in the protocol to evaluate the response of functional constipation patients with different severity levels to Vibrabot capsules.

Patients are considered eligible for this study if they meet the inclusion criteria and do not meet any of the exclusion criteria. This study plans to include 300 patients with chronic functional constipation to treat with Vibrabot capsules for at least 6 weeks or more.

The patients, based on their treatment needs and preferences, and after comprehensive consideration by clinical doctors, will undergo vibrating capsule treatment. After entering the study, patients should maintain stable dietary intake (including high-fiber diet, fiber supplements, probiotics, etc.) and exercise according to the recommendations of the constipation diagnosis and treatment guidelines.

4. Background of the Clinical Trial

Constipation is characterized by a decrease in bowel movements, dry and hard stools, and difficulty in defecation. With changes in diet, faster pace of life, and social psychological factors, the prevalence of chronic constipation is on the rise. The global incidence of chronic constipation is 14%, while the prevalence of chronic constipation in adults in China is 4.0% to 10.0%. The prevalence of functional constipation in China is 6%. The high-risk groups for constipation include the elderly, women,

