7.1 Trial Procedure

7.1.1 Trial Flow Chart

| | Visit 1 (0~1 day) | Visit 2 (Week 2 ±3 days) | Visit 3 (Week 4 ±3 days) | Visit 4 (Week 6±3 days) | Visit 5 (Week 10 ±3 days) |
|--|-------------------|--------------------------|--------------------------|-------------------------|---------------------------|
| Informed Consent | X | | | | |
| Baseline Information | X | | | | |
| Inclusion/Exclusion Criteria | X | | | | |
| Prescription Vibrabot capsule treatment/Medication treatment | X | X | X | | |
| Guide patients to use the "Vibrabot Health" Official Account | X | | | | |
| Fill out the Baseline Period Questionnaire (including scale) in the Official Account | X | | | | |
| Fill out the Daily Bowel Movement Questionnaire and Constipation Symptom Self-Assessment Scale and Assessment Scale for Quality of Life with Constipation | | X | X | X | X |
| Concomitant treatment | X | X | X | X | X |
| Adverse event | X | X | X | X | X |

正常诊疗流程筛选入组
Screening for Inclusion Based on Normal Diagnosis and Treatment Procedure

| | | | | | |
|--|---|---|---------------------------------------|---|-------|
| 功能性便秘分型(结肠传输时间、肛门直肠测压等) Functional Constipation Subtyping (Colon Transit Time, Anorectal Manometry, etc.) | 通过症状或问诊对便秘分型初步评估 Preliminary Assessment of Constipation Subtype Based on Symptoms or Interview | 可选 Optional | | | |
| 通过评估, 选择其他治疗方法 Selecting Alternative Treatment Methods through Assessment | 使用蔚通胶囊治疗 Treatment with Vibrabot Capsule | | | | |
| 患者填写问卷, 收集数据 Patients Complete Questionnaires to Collect Data | 沪惠保优惠或其他渠道购买 Purchase through Shanghai-Huibo Health Benefits or Other Channels | | | | |
| 不同使用频次 Different Frequency of Use | 不同疗程 Different Treatment Duration | 与其他方法联合治疗 Combination Treatment with Other Methods | 不同严重程度 Various Severity Levels | 对比其他方法治愈 Comparing Treatment Efficacy with Other Methods | |
| 各中心医生端数据共享 Data Sharing among Medical Centers | 定期学术会议讨论 Regular Academic Meetings for Discussion | | | | |
| 蔚通治疗方法不断优化, 形成专家共识 Continuous Optimization of the Vibrabot Treatment Method, Leading to Expert Consensus | 完成总结报告、科技论文, 研究生培养 Completion of Summary Report, Scientific Paper, and Training of Graduate Students | | | | |

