7.2 Effectiveness Evaluation Methods

7.2.1 Primary Efficacy Endpoints

After treatment, whether the response rate of patients using the Vibrabot vibrating capsules alone reaches 50%.

The definition of the responder is a patient with an average weekly increase of ≥ 1 complete spontaneous bowel movement (CSBM) compared to the baseline.

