7.2 Secondary Efficacy Endpoints

- 1) Proportion of constipated patients who use/do not use other constipation treatment methods during treatment and after the vibrating capsule treatment and at the end of follow-up;
- 2) Proportion of patients with an average increase of ≥ 1 CSBMs per week compared to the baseline period;
- 3) Proportion of respondents with an average of ≥ 3 SBMs per week during the treatment period;
- 4) Proportion of subjects with ≥ 3 SBMs per week and an increase of ≥ 1 CSBMs during at least 4 weeks of treatment compared to baseline;
- 5) Proportion of patients with an average increase of ≥ 1 CSBMs per week during the follow-up phase compared to the baseline period;
- 6) Proportion of patients with an average of ≥ 3 SBMs per week during the follow-up phase;
- 7) Proportion of patients with a reduction of ≥ 1 point in total PAC-QOL and PAC-SYM scores after treatment compared to the baseline period;
- 8) Proportion of patients with a reduction of ≥ 1 point in total PAC-QOL and PAC-SYM scores after follow-up compared to the baseline period;
- 9) Time of first use of laxative or enema after a course of vibrating capsule treatment (6 weeks);
- 10) Proportion of constipated patients (including different constipation types, occupations, age groups, BMI, gender, and baseline treatment status) responding to vibrating capsule treatment and at the end of follow-up.

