8.1 Statistical Analysis of the Population

Sample Size Calculation

H0: The effectiveness rate of vibrating capsule treatment for constipation $\leq 50\%$

H1: The effectiveness rate of vibrating capsule treatment for constipation $> 50\%$

In a single-group design, if the study goal is to evaluate the effectiveness of vibrating capsule

treatment for constipation and compare it with the expected 50% effectiveness rate, then a one-sample proportion test can be considered for sample size calculation.

Sample size calculation formula for single sample proportion test is:

$$n = \frac{\left[Z_{1-\alpha} \sqrt{P_0(1-P_0)} + Z_{\beta} \sqrt{P_T(1-P_T)} \right]^2}{(P_T - P_0)^2}$$

Where:

- (1) p is the overall expected success rate (here it is estimated that the effectiveness of treating constipation with vibrating capsules is 50%);
- (2) p_0 is the success rate under the null hypothesis (assuming a 40% success rate under the null hypothesis);
- (3) The probability of Type I error α is set to 0.05, and the probability of Type II error β is set to 0.2 (i.e., the statistical power is $1-\beta=0.8$);

At least 191 participants are needed for this study. Assuming a 20% loss to follow-up, the final sample size required is 239. Considering this is a real-world study and taking into account the outpatient volume of the participating center, it is planned to enroll 300 patients who will take vibrating capsules for 6 weeks, and at the same time, include ≥ 300 patients undergoing constipation treatment during the same period.

(1) Full Analysis Set (FAS) is the set of patients that is as close as possible to the ideal implied by the Intention-to-Treat principle. Specifically, in this trial, the FAS is the data set of all patients with baseline evaluation who take at least one capsule treatment/other treatment option. Missing data for primary efficacy endpoints in the FAS will be imputed according to certain rules while missing data for secondary efficacy endpoints will not be imputed.

(2) Per Protocol Set (PPS) is a subset of the FAS and refers to the set of subjects who meet the inclusion criteria, do not meet the exclusion criteria, complete the treatment, and have no protocol violations. Specifically, in this trial, the PPS includes the patients in the FAS who:

- a) complete the full treatment,
- b) meet the inclusion criteria and do not meet the exclusion criteria,
- c) have good compliance with capsule administration/other treatment, and

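### Section 8.1 sizes the trial for capsule treatment in general, but the primary endpoint covers capsule-alone patients, so the 80% power depends on a capsule-alone share that the plan does not state

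*Combined protocol and SAP*

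**What the plan says.** The primary endpoint (Protocol Summary and section 7.2.1) asks "whether the response rate of patients using the Vibrabot vibrating capsules alone reaches 50"%. It is therefore restricted to capsule monotherapy.

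The sample-size text in section 8.1 does not carry that restriction. H0 and H1 refer to capsule treatment of constipation as such, and the calculation gives 191 evaluable and 239 after 20% loss. The target then becomes "it is planned to enroll 300 patients who will take vibrating capsules for 6 weeks", plus at least 300 patients on other constipation treatment. The step from 239 to 300 is explained only by the real-world setting and outpatient volume.

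Other sections expect combination use:
- Section 3.2: patients "will undergo vibrating capsule treatment, other treatments, or combination therapy", according to preference and clinical judgement.
- Section 3.1: the purpose includes analysing response by "different severity, treatment status, capsule dosage, and combined medication to Vibrabot capsule".
- Section 7.1.1: the flow chart has an entry "Combination Treatment with Other Methods".
- Secondary endpoint 1: "Proportion of constipated patients who use/do not use other constipation treatment methods during treatment" and later.

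No section gives an expected capsule-alone share, a minimum capsule-alone number, or a rule to keep recruiting until 239 such patients are enrolled.

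**The concern.** The only test that the plan sizes is the one-sample test of the primary response rate. The population that enters that test and the population that fills the recruitment target are described differently. If combination users occupy places among the 300, recruitment can close at target with fewer than 239 capsule-alone patients enrolled and fewer than 191 evaluable. The primary result would then be less precise than the plan promises, and a non-significant finding would be hard to interpret. Once recruitment has closed, the gap cannot be repaired.

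**Working it through.** **Inputs.** From section 8.1: null rate 0.40 ("assuming a 40% success rate under the null hypothesis"), expected rate 0.50 ("here it is estimated that the effectiveness of treating constipation with vibrating capsules is 50"%), alpha 0.05, power 0.80, loss 20%, target 300. Two-sidedness is inferred: section 8.2 sets a two-sided 0.05, and only that value yields 191. The formula in 8.1 prints Z at 1−α and H1 is one-sided; a one-sided 0.05 would give 151. The capsule-alone share is not in the documents and is treated as an assumption over a range.

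**Step 1: reproduce the plan's figure.**
n = [1.960·√(0.40·0.60) + 0.842·√(0.50·0.50)]² / (0.50 − 0.40)² = 190.7, rounded up to 191.
191 / (1 − 0.20) = 238.75, rounded up to 239. Both figures match the plan.

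**Step 2: capsule-alone share needed.**
239 / 300 = 79.7%, so at most 300 − 239 = 61 of the 300 can be combination users.

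**Step 3: power by combination share.** The same formula, inverted, gives
power = Φ{[0.10·√n − 1.960·√0.24] / √0.25}.
The number n depends on how missing primary data are handled, and the plan conflicts here. Section 8.1 says that missing primary data in the Full Analysis Set will be imputed, under rules it does not give. Section 8.3 says that missing data are to be left unfilled. Both cases are shown. The imputed case takes n as all capsule-alone patients enrolled and assumes that imputation leaves the expected rate at 50%.

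| Combination share of the 300 | Capsule-alone enrolled | n after 20% loss | Power | n if imputed | Power |
|---|---|---|---|---|---|
| 0% | 300 | 240 | 88% | 300 | 94% |
| 20% | 240 | 192 | 80% | 240 | 88% |
| 30% | 210 | 168 | 75% | 210 | 84% |
| 40% | 180 | 144 | 68% | 180 | 78% |
| 50% | 150 | 120 | 61% | 150 | 70% |

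In the imputed case 191 is still reached while the capsule-alone share is at least 191 / 300 = 63.7%, that is, up to about 36% combination use.

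**Step 4: total capsule users needed for 239 capsule-alone.** 239 / share gives 266, 299, 342, 399 and 478 at shares of 90%, 80%, 70%, 60% and 50%.

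**Step 5: which hypothesis the 80% belongs to.** All these powers are for 40% versus 50%. The stated H0 is a rate of at most 50%, and the expected rate is also 50%. Against that null, at that rate, the probability of rejection does not exceed the type I error rate, whatever n is.

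**The case against.** The strongest reply is that the 300 may already be the capsule-only group. Section 3.2 names capsule treatment, other treatment and combination as three separate options, directly after describing both cohorts together. It then restates the 300 on their own as undergoing capsule treatment, with no mention of combination. On that reading all 300 are capsule-alone and power after 20% loss is about 88%. This reading is tenable. So is the other: a patient on combination therapy does take capsules, and response by combined medication is a study aim. The flow-chart entry does not settle which cohort it belongs to. The documents leave the matter open, and that is the defect.

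Second, 300 exceeds 239 by 61, a margin that absorbs about 20% combination use, or about 36% if missing primary data are imputed. This also stands, although the plan does not present the margin as an allowance for combination use.

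Third, section 8.1 never says that 191/239 are for capsule-alone patients; the link is inferred from the endpoint. That is so, but if 8.1 sizes all capsule users, the primary endpoint as worded has no sample size of its own. Either way the wording needs correction.

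A reader might infer that the trial is underpowered for its primary test. The documents do not support this, because they give neither the combination share nor a statement that combination patients fill places in the 300.

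**Conclusion.** The mismatch between section 8.1 and section 7.2.1 is in the text. Its effect on power is conditional. It arises only if combination patients count in the 300, and it takes power below 80% only if they exceed about 20% of the 300 (20% loss, no imputation) or about 36% (imputed, expected rate unchanged). Over 0% to 50% combination use, power for 40% versus 50% at two-sided 0.05 runs from 88% to 61% with loss and from 94% to 70% with imputation. The 80% is therefore not secured for the primary population, and no shortfall is shown.

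Nor would settling the population make the 80% apply to the hypothesis as stated, because the calculation tests against 40% and H0 says 50%. This is a point that should be fixed before recruitment closes. It does not show that the primary analysis will fail.

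**What to change.** In section 8.1:

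1. Word H0/H1 and the 191/239 for the capsule-alone population.
2. Define that population for analysis so that it matches the endpoint: no other constipation treatment used during the treatment period. The Visit 1 prescription alone is not enough, because section 7.1.2 allows other options to be prescribed at Visits 2 and 3.
3. State whether combination patients count in the 300, in the comparison group of at least 300, or separately.
4. Keep a running count of capsule-alone patients against 239, updated from the concomitant-treatment record at each visit.
5. If 300 stays a fixed total of any capsule users, state in advance the assumed capsule-alone share and the power at the resulting number, in place of an unconditional 80%. Power calculated afterwards from the number actually enrolled would not be a design safeguard.
6. Reconcile the null rate (H0 at most 50% versus 40% in the calculation) and redo the sample size on the reconciled value. Sections 8.1 and 8.3 should also be brought into line on missing primary data, since this decides which power column applies.

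The cost is protocol and SAP wording plus a count from data already collected. The downside is that the stated power may become less favourable, or the total to recruit larger (for example 342 capsule users at a 70% capsule-alone share).

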|-------------------------|--|
| | 
week during the follow-up phase compared to the baseline period;
 
6) Proportion of patients with an average of ≥ 3 SBMs per week during the follow-up phase;
 
7) Proportion of patients with a reduction of ≥ 1 point in total PAC-QOL and PAC-SYM scores after treatment compared to the baseline period;
 
8) Proportion of patients with a reduction of ≥ 1 point in total PAC-QOL and PAC-SYM scores after follow-up compared to the baseline period;
 
9) Time of first use of laxative or enema after a course of vibrating capsule treatment (6 weeks);
 
10) Proportion of constipated patients (including different constipation types, occupations, age groups, BMI, gender, and baseline treatment status) responding to vibrating capsule treatment and at the end of follow-up.
 |
| Safety Endpoints | 
 1. The incidence (%) and the number of device-related adverse events (AEs) and serious adverse events (SAEs); 2. The incidence (%) and the number of device defects. |

1. About the Sponsor

| | |
|--------------|---|
| Name: | ANKON Medical Technologies (Shanghai) Co., Ltd. |
| Address: | [name] |
| Contact No.: | [name] |

2. List of All Clinical Trial Sites and Investigators in the Multi-Center Clinical Trial

| Site No. | Clinical Trial Site Name | Principal Investigator | Professional Title |
|----------|---|------------------------|----------------------------|
| 01 | The First Affiliated Hospital of Navy Medical University (Shanghai Changhai Hospital) | [name] | Chief Physician, Professor |

| | | | |
|----|---|----------------|----------------------------|
| 02 | Ruijin Hospital, Shanghai Jiao Tong University School of Medicine | [name] | Chief Physician, Professor |
| 03 | Shanghai Tongji Hospital | [name] | Chief Physician |
| 04 | Shanghai Tenth People's Hospital | [name] | Chief Physician, Professor |
| 05 | Shanghai First People's Hospital | [name] | Chief Physician |
| 06 | Shanghai Sixth People's Hospital | [name] | Chief Physician, Professor |
| 07 | Shanghai Ninth People's Hospital | [name] | Chief Physician |
| 08 | Shanghai Yangpu District Central Hospital | [name] | Chief Physician |
| 09 | Shanghai Pudong New Area Gongli Hospital | [name] | Chief Physician |

3. Purpose and Content of the Clinical Trial

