6.2 Exclusion Criteria

1. People who are not eligible for surgery or refuse to undergo any abdominal surgery;
2. People with known or suspected gastrointestinal obstruction, stenosis, diverticulum, bleeding, malformation, and fistula.
3. People allergic to polymeric materials;

4. People implanted with cardiac pacemakers and using gastrointestinal pacemakers;
5. People with abdominal aortic aneurysms, gastrointestinal vascular lesions, ulcers, and lesions with bleeding tendencies.
6. People with dysphagia;
7. Pregnant women;
8. People with severe depression and anxiety and severe acute gastrointestinal lesions.
9. People with other conditions, so the investigator considers them not eligible for this study.

7 . Overall Design

This study is a multi-center, prospective cohort study based on real-world clinical trial design, planning to include 300 patients with chronic functional constipation to treat with Vibrabot capsules, and concurrently include ≥ 300 patients with functional constipation to treat by other methods.

During the study, it is necessary to collect the patient's basic information, baseline constipation status and treatment information, capsule intake during treatment, and concomitant medication. During the treatment phase, patients follow the doctor's advice to receive Vibrabot capsule treatment and maintain stable dietary intake and exercise according to the constipation diagnosis and treatment guidelines.

During the study, the patients need to scan the QR code or search for the electronic questionnaire "Vibrabot Health" Official Account on WeChat, and fill in the relevant information during the treatment in the electronic questionnaire in a timely and truthful manner. The treatment effect of the patients is evaluated by assessing the number of occurrences of spontaneous bowel movements (SBM) and complete spontaneous bowel movements (CSBM).

Note:

[figure not shown]
Spontaneous bowel movement: No medication used within 24 hours before bowel movement.

Spontaneous bowel movement: No medication was used within 24 hours before defecation, and there is a feeling of complete fecal evacuation.

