7.3 Safety Evaluation Method

The safety is evaluated by the occurrence of device-related adverse events (AEs) and device-related serious adverse events (SAEs) throughout the study period.

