- d) have a complete evaluation of the primary efficacy endpoints.

The PPS is a secondary population for efficacy analysis and is used for sensitivity analysis during efficacy analysis.

(3) Safety Data (SS) includes all randomized patients. It is the primary population for safety analysis.

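### The safety set is defined by randomization in a non-randomized cohort, and neither the denominator for device events nor the cut-off for device-related is stated, so the place of capsule retention in the endpoint rests on case-by-case attribution

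*Combined protocol and SAP*

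**What the plan says.** **Safety population.** Section 8.1, item (3): "Safety Data (SS) includes all randomized patients. It is the primary population for safety analysis".

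**Design.** Section 7 (Overall Design): "This study is a multi-center, prospective cohort study based on real-world clinical trial design". Section 3.2 says that treatment is chosen "based on their treatment needs and preferences, and after comprehensive consideration by clinical doctors", and that patients "will undergo vibrating capsule treatment, other treatments, or combination therapy". No section describes randomization. By contrast, the full analysis set in Section 8.1 is based on exposure: it takes patients with a baseline evaluation "who take at least one capsule treatment/other treatment option".

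**Safety endpoints.** The Protocol Summary lists the incidence and number of device-related adverse events and of serious adverse events; its wording leaves open whether the serious events must also be device-related. It then lists "The incidence (%) and the number of device defects". Section 7.3 is narrower: "The safety is evaluated by the occurrence of device-related adverse events (AEs) and device-related serious adverse events (SAEs) throughout the study period".

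**Causality.** Section 13.1.2 grades events on five levels, from *definitely related* to *unrelated*. No section says which levels make an event device-related for the endpoint.

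**Retention.** Section 9.2 singles out capsule retention as the adverse event of greatest concern and cites a rate of 0.73% (95% CI 0.59% to 0.89%). It then states that retention arises from an undetected condition in the patient, and not from the capsule or its quality.

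**The concern.** The safety result is to be reported as a percentage, and two things that determine it are not fixed in advance.

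The first is the denominator. A rule that selects randomized patients selects nobody here. Replacing the word with enrolled or treated gives a usable set, but that set spans both cohorts. Device-related events and device defects can arise only in patients who took a capsule, and the plan does not say that these patients, including those on combination therapy, are the base for the percentage.

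The second is the numerator. Without a causality cut-off, each investigator's grading and a later decision on which grades count determine what enters the endpoint. This matters most for retention, which the plan ranks as the leading concern and also explains in advance as not caused by the capsule. Whether it shows in the headline safety percentage may then depend on how individual cases are attributed across nine sites.

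**Working it through.** The plan gives no safety-set size and no safety precision, so there is no stated figure to reproduce. The check has three parts.

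**1. Who is in the safety set**

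- Section 8.1 selects on randomization. Sections 3.2 and 7 describe allocation by need, preference and clinical judgement. Literal membership: 0.
- Likely repair: read the word as enrolled or as treated. Inputs: 300 planned capsule patients (Section 8.1); two events (illustrative); 5% or 10% never treated (assumed).
  - Enrolled: 2/300 = 0.67%.
  - Treated, 5% never treated: 300 × 0.95 = 285; 2/285 = 0.70%.
  - Treated, 10% never treated: 300 × 0.90 = 270; 2/270 = 0.74%.
- The choice between these two repairs is therefore minor. Neither says whether the base for device outcomes is every capsule-exposed patient or only those on the capsule alone, the group in which the primary efficacy endpoint is defined.

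**2. How retention would be graded under Section 13.1.2**

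- *Possibly related* asks for close timing, support in the literature, and other factors such as underlying disease that cannot be ruled out. Retention fits: it follows swallowing a capsule, Section 9.2 cites a published rate, Section 10 names it as the usual risk of capsule devices, and underlying disease is the stated suspicion.
- *Unrelated* lists four features: no reasonable time sequence, not a type of reaction known for the device, explicable by the patient's condition or another reason, and resolution once that reason is removed. Retention fails the first two. It meets the third on Section 9.2's own account.
- The *unrelated* list has no conjunction, so the text does not say whether all four features are needed. Read as a whole, the section leans towards at least *possibly related*, but it does not settle the grade. Nor does any section say that *possibly related* counts as device-related.

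**3. What attribution could do to the percentage (illustration only)**

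Inputs: 300 capsule patients; rate p = 0.0073 (0.0059 to 0.0089) from Section 9.2. Assumptions: the rate is per patient and applies to this device and population. The document states neither.

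- Expected retentions, 300 × p: 300 × 0.0073 = 2.19 (300 × 0.0059 = 1.77; 300 × 0.0089 = 2.67).
- Chance of at least one, 1 − (1 − p)^300: 0.889 (0.831 to 0.932).
- If the exclusion criteria halved the risk (assumed), p = 0.00365: 300 × 0.00365 = about 1.1 expected; chance of at least one 1 − (1 − 0.00365)^300 = 0.67.
- Two cases counted as device-related: 2/300 = 0.67% (exact 95% CI 0.08% to 2.39%).
- The same two cases rated unrelated, with no other event: 0/300 = 0% (upper limit of the exact two-sided 95% CI 1.22%).

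**The case against.** **What the other side can say.** The word in Section 8.1 is a template slip that any analyst would correct, and the obvious corrections barely move the rate. The Protocol Summary asks for event numbers beside percentages, so a reader could recompute a rate. The safety analysis is descriptive, with no hypothesis. On causality, the labels suggest a natural cut: three grades affirm a relation and two do not. Requiring all four features of *unrelated* is the more natural reading, since treating them as alternatives would absorb much of *possibly related*. Section 9.2 is risk narrative, not a grading rule. Section 13.1.3 requires every adverse event to be recorded. A retention meeting the serious definition in Section 13.3 is reported under Sections 13.4.1 and 13.4.2 with no filter on causality.

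**What stands.** Most of this is right, and it limits the point. It does not remove it. Reported counts help only for events already accepted as device-related; a natural cut-off is not a stated one; and a recorded event is not an endpoint event.

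**Stronger readings that the documents do not support.**

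- A reader might infer that device events will be divided by both cohorts, which would halve every rate if the comparison group were also 300. The plan does not propose this.
- A reader might infer that the plan removes retention from the safety endpoint. No section says so, and the grading text leans the other way.
- A reader might apply 0.73% to every capsule swallowed and expect far more cases. The unit of the rate is not given, and Section 9.2 attributes retention to the patient's condition, so capsules in one patient cannot be treated as independent.

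**Conclusion.** The point holds in limited form. The primary safety population is defined by an event that does not occur in this study; this is a definite error with a small numerical effect under the likely repairs. The more useful part is what those repairs leave unsaid: the denominator for device outcomes and the causality grades that count.

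For retention, the size is about two cases in 300 capsule patients, reading as 0.67% or 0% by attribution alone, if the cited rate is per patient and transfers to this trial. Confidence is high on the wording error and the missing cut-off. It is lower on retention, because the documents leave room for it to be graded out of the endpoint but do not say that it will be. Such an event would still appear in the adverse event records and, if serious, in the safety reports. The primary efficacy analysis is not affected.

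**What to change.** Before the safety data are analysed:

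1. In Section 8.1, define the safety set as all patients who received at least one capsule or other study treatment, analysed by treatment received.
2. Name capsule-exposed patients, alone and in combination, as the denominator for device-related events and device defects.
3. In Section 7.3 and the Protocol Summary, report all recorded adverse events and serious adverse events, with device-related events as a subset. State the causality cut-off (for example, *possibly related* or higher) and whether serious events must be device-related to count.
4. Report capsule retention as a named event, counted whatever its attribution.
5. Reconcile the Protocol Summary and Sections 7.3, 9.2 and 13.1.2 on how retention is classified, including whether the features under *unrelated* must all be present.

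**Cost.** The changes are a few sentences in the Protocol Summary and Sections 7.3, 8.1, 9.2 and 13.1.2. Adverse events are already collected at every visit (Section 7.1.1) and all are to be recorded (Section 13.1.3), so no new visit or data item is needed. The downsides are slightly more reporting, possibly a less favourable event rate, and ethics committee approval of the amended wording (Sections 12.1.2 and 14).
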